Clinical Study Protocol			
Rosuvastatin			
DM-CRESTOR-0002			
2.1			
28-March-2007			

A double blind, double dummy, phase IV, randomized, multicenter, parallel group, placebo control trial to evaluate the effect of rosuvastatin on triglycerides levels in Mexican hypertriglyceridemic patients.

Sponsor:

AstraZeneca Mexico, Mexico City.

AstraZeneca Site representative

> [name] Project Physician

Date

The following Amendment(s) and Administrative Changes have been made to this protocol since the date of preparation:

Amendment No.	Date of Amendment	Local Amendment No:	Date of Local Amendment
		1	28.03.07
Administrative change No.	Date of Administrative Change	Local Administrative change No.	Date of local Administrative Change
		NA	NA

PROTOCOL SYNOPSIS

A double blind, double dummy, phase IV, randomized, multicenter, parallel group, placebo control trial to evaluate the effect of rosuvastatin on triglycerides levels in Mexican hypertriglyceridemic patients.

National Co-ordinating Investigator

[name]

Study centres and number of patients planned

The study will be conducted in approximately 330 randomised patients. They will be recruited from approximately 10 to 12 centres around Mexico and it is planned that centres should randomise approximately 30 patients each. The approximate numbers of randomised patients will be recruited from Mexico City (150 patients), Monterrey (90 patients), Guadalajara (60 patients), Toluca (30 patients) and San Luis Potosi (30 patients). Centres may be discontinued from the study if recruitment rates are poor and new centres will be added if necessary to achieve recruitment goals. Recruitment will be competitive and centres will stop enrolment when enough patients are screened to provide the projected number of randomised patients.

Phase of development

IV

Study periodEstimated date of first patientMay 2007enrolled

Estimated date of last patient February 2008 completed (defined as date of the last visit of the last patient)

Objectives

Primary Objective

The primary objective of this study is to evaluate the efficacy of rosuvastatin in reducing triglycerides (TG) levels in hypertriglyceridemic (HTG) Mexican patients from baseline to week 8.

Secondary Objectives

The secondary efficacy objectives of the study are as follows:

- 1. To evaluate the efficacy of RSV on:
 - a. Reducing non-HDL-C levels.

- 2. To evaluate the efficacy of RSV in improving atherogenic lipid profile on:
 - a. Reduction of low-density lipoprotein cholesterol (LDL-C)
 - b. Reduction of total cholesterol (TC)
 - c. Increase of high-density lipoprotein cholesterol (HDL-C)
 - d. Changes in apolipoprotein A1 (ApoA-1), apolipoprotein B (ApoB) and
 - e. Changes in TC/HDL-C, LDL-C/HDL-C, nonHDL-C/HDL-C and ApoB/ApoA-1 index, from baseline to week 8.
- 3. To determine the efficacy of RSV in reducing other CV risk markers: high-sensitive C-reactive protein (hsCRP) from baseline to week 8.

Study design

This is a randomised, double-blind, double dummy, parallel-group, placebo control, national, multicentre, phase IV study to evaluate the effects of rosuvastatin 10 mg, rosuvastatin 20 mg and placebo over 8 weeks on triglycerides levels in hypertriglydemic patients.

Patients will enter a 5-week lead-in period, after which eligible patients will be randomised to receive treatment with either rosuvastatin 10 or 20 mg/day or placebo once daily for 8 weeks.

Target patient population

Male and female patients aged ≥ 18 years with basal triglycerides levels between ≥ 200 and < 800 mg/dl (regardless LDL-C levels), statin naïve. Patients will be considered statin naïve when they had, at least, 6 months or more without taking any statin therapy for before visit 1.

Investigational product, dosage and mode of administration

Investigational product: rosuvastatin 10 and 20 mg

Rosuvastatin 10 mg: One tablet of rosuvastatin 10 mg + one tablet of placebo matching rosuvastatin 20 mg, once daily in oral tablet form

Rosuvastatin 20 mg: One tablet of rosuvastatin 20 mg + one tablet of placebo matching rosuvastatin 10 mg, once daily in oral tablet form

Placebo: One tablet of placebo matching rosuvastatin 10 mg and one tablet of placebo matching rosuvastatin 20 mg, once daily in oral tablet form

Duration of treatment

Patients will initially enter a 5-week lead-in period during which they will undergo Therapeutic Life Stile Change (TLC) advisory according to NCEP ATPIII guidelines (See Appendix F). In this period no lipid lowering therapy will be allowed.

At the end of the 5-week lead-in period, during visit 2, a new TG analysis will be made and eligible patients (those with TG levels between \geq 200 mg/dl and <800 mg/dl on visit 2), will be randomised (on visit 2.1) with a 1:1:1 randomisation ratio to receive blinded treatment with either rosuvastatin 10 mg, rosuvastatin 20 mg or placebo. During the 8 weeks of the randomised treatment period, patients will continue with the TLC.

Clinical Study Protocol Drug Substance Rosuvastatin Study Code DM-CRESTOR-0002 Edition Number 2.1 Date 28-March-2007

End Points

– **Primary end point:**

1. Change (reduction) in triglycerides levels from baseline to end of treatment (week 8).

- Secondary end points:

- Change (reduction) in no-HDL-C from baseline to end of treatment,.
- Change in LDL-C; TC; ApoB; ApoA1; ApoB/ApoA1; TC/HDL-C; LDL-C/HDL-C, non-HDL-C/HDL-C index from baseline to the end of treatment.
- Change in hsCRP levels from baseline to the end of treatment.

Patient reported outcomes (PROs)

- There are no patient reported outcomes for this study

- Health economics

- There are no health economic evaluations in this study

– Pharmacokinetic

- There are no pharmacokinetic outcomes for this study

– Pharmacodynamic

- As stated in the protocol

– Safety

- Safety evaluation, as determined by the incidence and severity of adverse events and abnormal laboratory values
- Genetics
 - There are no genetics outcomes for this study

Statistical methods

Lipids and lipoproteins are: Triglycerides, no-HDL-C, LDL-C, total cholesterol, HDL-C, ApoA1, and ApoB levels and ApoB/ApoA1, no-HDL-C/HDL-C and LDL-C/HDL-C indexes. Baseline for calculating percent change in a lipid or lipoprotein will be the values from the randomization visit (visit 2.1).

The following analyses will be performed for TG:

- Last observation carried forward (LOCF) on the ITT (Intention to treat) population for primary and secondary endpoints at week 8. This will be the primary analysis.
- Observed data on the per Protocol (PP) population for primary and secondary endpoints at week 8.

Initially a Friedman analysis will be performed, then, for comparing basal state against 8 week, inside each group, a Willcoxon test will be performed. For comparing each one of Rosuvastatin groups against placebo group at week 8 a U Man Whitney test will be done. Also, the percentage of reduction –week 8 minus basal- obtained in the placebo group will be contrasted against the percentage of reduction in each one of the Rosuvastatin groups using a U Man Whitney test. In all the cases a p < 0.05 will be considered significant.

Lipids (other than TGs), apolipoproteins and hsCRP comprising secondary endpoint (1, 2 and 3) will be analysed in a similar way.

Adverse events can occur in the dietary lead-in phase and/or the randomised phase of the study. The latter phase will include the period up to 30 days after the last dose of study medication. All adverse events will be classified according to the following:

- Reported during the dietary lead-in period
- Treatment emergent. This is further categorized as:
 - Ongoing from the dietary lead-in period and subsequently worsening during the randomised period, and
 - Starting during the randomized period.

All adverse events will be categorized by the body system and preferred term assigned to the event using National Medical Terminology Officially Accepted terms and listed for each subject. For subjects in the dietary lead-in safety population events occurring during the dietary lead-in phase will be summarised by frequency; in the randomized safety population treatment emergent events will be reported as frequencies in each treatment group. Frequencies of adverse events leading to withdrawal from the randomized period will also be tabulated and reported by treatment group. Adverse events leading to death, serious adverse events and drug related adverse events would be presented similarly.

TABLE OF CONTENTS

PAGE

	TITLE PAGE	1
	PROTOCOL SYNOPSIS	2
	TABLE OF CONTENTS	6
	LIST OF ABBREVIATIONS AND DEFINITION OF TERMS	10
1.	INTRODUCTION	13
1.1	Background	13
1.2	Rationale for this study	14
2.	STUDY OBJECTIVES	14
2.1	Primary objective	14
2.2	Secondary objectives	14
3.	STUDY PLAN AND PROCEDURES	
3.1	Overall study design and flow chart	15
3.2	Rationale and risk/benefit assessment	20
3.2.1	Rationale for study design and control group	
3.2.2	Risk/benefit and ethical assessment	
3.3	Selection of study population	
3.3.1 3.3.2	Study selection record Inclusion criteria	
3.3.3	Exclusion criteria	
3.3.4	Restrictions	

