Co-ordinating investigator	A Co-ordinating Investigator is the investigator that coordinates the investigators and/or activities nationally.		
LDL	Low-density lipoprotein		
LDL-C	Low-density lipoprotein cholesterol		
LOCF	Last observation carried forward		
mg	Milligram		
mg/dL	Milligram per decilitre		
MI	Myocardial infarction		
mL	Millilitre		
NCEP	National Cholesterol Education Program		
Non-HDL-C	Non-high-density lipoprotein cholesterol		
OCT	Oral contraceptive therapy		
OAE	Other Significant Adverse Event (i.e., adverse events of particular clinical importance, other than SAEs and those AEs leading to discontinuation of the patient from study treatment; see definition in Section 4.8.1.1).		
Outcome variable	A variable (usually a derived variable) specifically defined to be used in the analysis of a study objective.		
PD	Pharmacodynamic		
PI	Prescribing Information		
РК	Pharmacokinetic		
PP	Per-protocol		
Principal investigator	A person responsible for the conduct of a clinical study at an investigation study site. Every investigational study site has a principal investigator.		
SAP	Statistical analysis plan		
SAS	Statistical Analysis System [®]		
SAE	Serious adverse event (see definition in Section 4.8.1.1).		
SD	Standard deviation		
SGOT	Serum glutamic oxaloacetic transaminase (=AST)		
SGPT	Serum glutamic pyrivic transaminase (=ALT)		
ST	Study team		
Statin naïve	Patients will be considered statin naïve if they had, at least, 6 month or more without taking any statin treatment prior to visit 1.		
TC	Total cholesterol		
TG	Triglycerides		

Clinical Study Protocol Drug Substance Rosuvastatin Study Code DM-CRESTOR-0002 Edition Number 2.1 Date 28-March-2007

Abbreviation or special term	Explanation
TIA	Transient Ischaemic Attack
TLC Diet	Therapeutic Lifestyle Changes Diet
TSH	Thyroid-stimulating hormone
ULN	Upper limit of normal
SDV	Source data verification
VLDL	Very-low-density lipoprotein
VLDL-C	Very-low-density lipoprotein cholesterol

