3.2 Rationale and risk/benefit assessment

3.2.1 Rationale for study design and control group

The NCEP ATPIII recommendations for patients with HTG are first to lower the LDL-C levels and then the TG levels in order to reduce the CV risk(2). In HTG patients, a drug that can reduce both parameters will have an additional benefit.

Statins have been shown convincingly to reduce cardiovascular morbidity and mortality in multiple large outcomes trials in various populations, with substantial reductions in LDL-C and TG levels in non-diabetic and diabetic patients (22, 23). Statins reducing TG levels are known to be directly related to the LDL-C reduction potency meaning that more potent statins should be more effective in lowering TG. For this reason, the current study will use one of the most potent statins (RSV) and will test its efficacy in reducing TG levels in Mexican HTG patients.

This study is using a placebo arm as a control. Patients that are currently on statin therapy cannot enter the study because it would not be ethic to stop their statin therapy. As we are using a placebo arm, the study will only last for 8 weeks and all patients will be treated with TLC diet as appropriate. After completing the study period, all patients will be offer to continue with active commercially available therapy determine by the investigator experience.

The 5-week lead in period will serve as a washout period of possible residual effects of preexisting lipid lowering therapy (other than statins) use, which is important to establish a reliable baseline to determine the change from baseline during double-blind treatment.

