3.3.2 Inclusion criteria

For inclusion in the study lead-in period at Visit 1, patients must fulfil all of the following criteria:

- 1. Provision of written informed consent
- 2. Male or female aged ≥ 18 years
- 3. Statin naïve patients (as defined by protocol)
- 4. No previous lipid lowering treatment other than statins 6 months before visit 1
- 5. Fasting TG concentrations at visit 1 of: $\geq 200 \text{ mg/dL}$ and < 800 mg/dlL
- 6. Fasting LDL-C concentrations at visit 1 of: $\geq 100 \text{ mg/dL}$ and $\leq 190 \text{ mg/dL}$

(Note: the results of the above laboratory sample will not be available at visit 1 to make the eligibility decision. Therefore, if the subject's medical history meets the eligibility criteria the subject can enter into the dietary lead-in period of the study. However, when the laboratory results are available, if the results do not meet the above criteria, the subject should be contacted and discontinued from the study)

- 7. Fasting TG concentrations at visit 2 of: \geq 200 mg/dL and < 800 mg/dlL
- 8. Fasting LDL-C concentrations at visit 2 of: $\geq 100 \text{ mg/dL}$ and $\leq 190 \text{ mg/dL}$
- 9. Subjects willing to follow all study procedures including the attendance at clinics for scheduled study visits, fasting prior to clinic visits (Visits 1, 2 and 3 blood draws) and compliance with study treatment regimen.

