3.3.3 Exclusion criteria

Any of the following is regarded as a criterion for exclusion from the study:

- 1. LDL-C levels \geq 190 mg/dL
- 2. History of any other lipid lowering therapy 6 months before visit 1.
- 3. Subjects considered to be unstable after a myocardial infarction, unstable angina, myocardial revascularisation or a transient ischemic attack (TIA) or stroke
- 4. Subjects awaiting a planned myocardial revascularization prior to starting the study (ie, planned prior to visit 1)
- 5. Severe congestive cardiac failure (New York Heart Association [NYHA] Class IIIb or IV)
- 6. Uncontrolled diabetes diagnosis by $HbA_{1c} \ge 8\%$, or fasten oral glucose $\ge 150 \text{mg/dL}$.
- 7. History of malignancy (unless a documented disease-free period exceeding 5 years is present) with the exception of basal cell or squamous cell carcinoma of the skin. Women with a history of cervical dysplasia would be permitted to enter the study provided they have 3 consecutive clear Papanicolaou (Pap) smears.
- 8. Uncontrolled hypothyroidism defined as a thyroid stimulating hormone (TSH) >1.5 times the upper limit of normal (ULN) at Visit 1. (This is due to the relationship between myopathy and patients with hypothyroidism undergoing statin therapy)
- 9. History of homozygous familial hypercholesterolaemia. (Due to the lipid levels exhibited by this group of patients they are considered unsuitable for this study as they often require combination lipid-lowering therapy)
- 10. History of alcohol, or drug abuse within the last 5 years.
- 11. Current active liver disease [alanine aminotransferase (ALT) (SGPT) > 3 x ULN] or severe hepatic impairment
- 12. Unexplained rise of creatine kinase (CK) \ge 3 x ULN at visit 1

- 13. Serum creatinine > 176 μ mol/L (2.0 mg/dL) at visit 1
- 14. Pregnancy, breast-feeding, and women of childbearing potential who are not using a reliable contraception method.
- 15. Subjects previously screened for this study and/or subjects randomised to treatment who subsequently withdraw cannot re-enter this study.
- 16. Patients participating in any other clinical trial.
- 17. Serious or unstable medical or psychological conditions that, in the opinion of the investigator, would compromise the subject's safety or successful participation in the study.

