3.7 Pre-study, concomitant and post-study treatment(s)

Patients must not have been treated with any statin 6 months prior to Visit 1.

Patients must not have been treated with a lipid lowering therapy (other than statin) 6 months before visit 1.

All disallowed medications should be stopped on entry to the study (or 6 months before if it is a lipid-modifying drugs other than statins), and are disallowed during the lead-in period and whilst the patient is receiving study medication. With the exception of lipid-modifying agents (which will affect the study objectives and baseline lipid characteristics), the listed medications are disallowed on the basis of safety concerns. In particular there is a risk of myopathy with antibiotics, antifungals and immunosuppressants (due to possible increases in plasma levels).

Other medication, which is considered necessary for the patient's safety and well being, may be given at the discretion of the investigator(s), provided that they do not conflict with the disallowed medication in Table 4. The administration of all medication (including investigational products) must be recorded in the appropriate sections of the CRF. If antacids are required, they should be taken 2 hours after dosing with study medication.

Class of drug	Generic name
Antibiotics	Erythromycin base, clarithromycin
	Erythromycin ethyl succinate, acetyl sulfisoxazole
Antifungal (chronic systemic use)	Fluconazole
	Ketoconazole
	Itraconazole
Antidiabetics	Insulin
	PPAR α/γ agonists (glitazones)
Lipid regulation	Gemfibrozil
	Fenofibrats
	Benzofibrats
	Niacin
	Ezetimibe
	Atorvastatin
	Lovastatin
	Pravastatin
	Rosuvastatin (except for study medication)
	Simvastatin
	Fluvastatin
	Omega 3
Immunosuppresants	Cyclosporin
	Lymphocyte immune globulin
	Rho(d) immune globulin
	Azathioprine sodium
	Muromonab-CD3
	Prograf (FK-506)
	Cellcept (mycophenolate mofetil)
	Oral or intravenous corticosteroids

Table 4Disallowed concomitant medication

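### The six-month statin-naïve rule admits former statin users whatever their reason for stopping, and no exclusion covers statin hypersensitivity or a past statin muscle or liver reaction

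*Protocol*

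**What the plan says.** The statin rule appears four times in the protocol, and it concerns time only.

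- Synopsis, Target patient population: "Patients will be considered statin naïve when they had, at least, 6 months or more without taking any statin therapy" before Visit 1.
- List of abbreviations and definition of terms: "Patients will be considered statin naïve if they had, at least, 6 month or more without taking any statin treatment prior to visit 1".
- Section 3.3.2, criterion 3, refers back to that definition: "Statin naïve patients (as defined by protocol)".
- Section 3.7: "Patients must not have been treated with any statin 6 months prior to Visit 1".

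Section 3.2.1 explains why current users are kept out: "Patients that are currently on statin therapy cannot enter the study because it would not be ethic to stop their statin therapy". That reason does not apply to people who have already stopped.

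Section 3.3.3 lists 17 exclusions. Three of them bear on statin muscle or liver risk. Criterion 8 excludes a raised TSH and gives the reason: "This is due to the relationship between myopathy and patients with hypothyroidism undergoing statin therapy". Criterion 11 reads "Current active liver disease [alanine aminotransferase (ALT) (SGPT) > 3 x ULN] or severe hepatic impairment". Criterion 12 excludes an unexplained CK of at least 3 x ULN at Visit 1. Criterion 17 is a general clause on serious or unstable conditions, left to the investigator's opinion.

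**The concern.** Statin naïve here does not mean never exposed. It includes anyone who stopped a statin at least six months ago, and intolerance is one possible reason for stopping. The protocol treats statin muscle and liver toxicity as an entry matter, through TSH, ALT and CK, but only as the patient stands at screening. Someone with a known statin allergy, or with a serious muscle or liver reaction that has since resolved, can have normal values at screening and pass.

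At stake is the safety of a small, uncounted group of patients. They could be given a statin again, under blind, and whether that happens would depend on individual judgement at 10 to 12 centres.

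**Working it through.** The protocol states no figure to reproduce. The check sets the entry rules against the protocol's own safety rules, followed by one line of arithmetic.

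**1. Does any statement of the statin rule depend on the reason for stopping?** No. All four refer only to the six-month interval.

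**2. Does any exclusion cover a past reaction?** The criteria in 3.3.3 run from 1 to 17 without a gap. Statin or rosuvastatin hypersensitivity is named in 0 of 17, and a previous statin muscle or liver reaction in 0 of 17.

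**3. How do the entry tests compare with the stopping rules?**

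| Risk | Entry test (3.3.3) | Rule on study drug (3.3.5.1) |
|---|---|---|
| Muscle | Unexplained CK ≥3 x ULN at Visit 1; TSH >1.5 x ULN at Visit 1 | Stop for unexplained muscle symptoms with CK >10 x ULN |
| Liver | Current active disease with ALT >3 x ULN, or severe hepatic impairment | Withdrawal recommended for ALT 3 x ULN on two consecutive occasions more than 48 hours apart, with no obvious reversible cause |

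A patient who had either right-hand event on an earlier statin, and has recovered, is caught by nothing in the middle column.

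**4. Do the other provisions close the gap?**

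- Criterion 17 needs a serious or unstable condition. A resolved reaction is not plainly either.
- Section 3.3.5.1 allows discontinuation at any time for safety reasons. It can act in the lead-in, but it is discretionary.
- Section 3.2.2 points to the prescribing information for further information. It is not an eligibility rule.
- Section 3.3.5.2 deals with contraindicated study drug only in patients already randomised incorrectly. A patient who meets every written criterion was not randomised incorrectly.
- Prior medication (Table 1, note b) and significant medical history (section 4.3) are collected, but no criterion acts on a past statin reaction.

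**5. When would a recurrence be seen?** Table 1 schedules CK and liver tests at weeks -5, -1 and 8. Drug is dispensed at week 0, and the next scheduled visit is week 8. Between the two, the CK and ALT stopping rules can act only if the patient reports symptoms or an unscheduled test is done.

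**6. Exposure.** With 1:1:1 allocation to rosuvastatin 10 mg, 20 mg or placebo:

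P(rosuvastatin) = (1 + 1)/(1 + 1 + 1) = 2/3

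If k such patients were among the 330 randomised, the expected number on rosuvastatin is 2k/3. The protocol does not give k, so the values below are assumptions for illustration.

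| Assumed k | Expected on rosuvastatin, 2k/3 |
|---|---|
| 1 | 0.67 |
| 3 | 2.0 |
| 10 | 6.67 |

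**The case against.** The six-month definition is consistent wherever it appears and contradicts nothing, so the complaint comes down to one line absent from 3.3.3. This is a phase IV trial of a marketed drug. Investigators are referred to the prescribing information, and section 3.3.5.2 uses the idea of a contraindication without defining it, so the meaning presumably comes from there. The prescribing information, the CRF and Appendices B, D and E are not shown and may deal with re-exposure. CK is repeated and a full hepatic profile taken at Visit 2, with eligibility rechecked before randomisation. The history taken at Visit 1 gives the investigator a chance to learn of an earlier reaction, and criterion 17 names the subject's safety as its test. The stopping rules govern events during this study and carry qualifiers; they do not say that a recovered patient is ineligible for good. Finally, the counts of 1, 3 and 10 are invented.

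Much of this is right as far as it goes. A careful investigator may well refuse such a patient, re-exposure is a clinical judgement, and the counts only restate the allocation ratio. That limits the severity. It does not close the gap: repeat tests at Visit 2 still measure the present state, a pointer to a label is not an entry criterion, and by their titles Appendices D and E cover management of raised transaminases and of muscle symptoms and CK, not eligibility. The qualifiers in the stopping rules matter and should be carried into any threshold borrowed from them.

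**Conclusion.** The concern holds. As written, a patient with a known statin allergy, or a resolved significant muscle or liver reaction to an earlier statin, meets every entry criterion. That patient has a 2/3 chance of up to eight weeks of rosuvastatin at 10 or 20 mg with no scheduled laboratory check before the final visit.

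The importance is minor to moderate and concerns patient safety alone. The number of such patients and the risk of recurrence are not in the documents, and neither is claimed here. The conclusion rests on the protocol's own use of statin muscle and liver risk as grounds for exclusion and for stopping, and on the text available. If the prescribing information or an unseen appendix bars such patients and sites apply it, the practical gap is smaller. Confidence is medium for that reason.

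**What to change.** Keep the six-month definition and add one exclusion to 3.3.3. Suggested wording:

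*Known hypersensitivity to rosuvastatin or another statin, or a previous statin stopped because of a clinically significant muscle or liver reaction (for example, otherwise unexplained muscle symptoms with CK >10 x ULN, or ALT 3 x ULN on two consecutive occasions more than 48 hours apart with no obvious reversible cause). Mild myalgia alone does not exclude.*

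The sponsor's physicians should settle the final threshold.

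Add one CRF item at Visit 1 asking about any past statin, not only in the last six months, and the reason for stopping. The eligibility recheck at Visits 2 and 2.1 (Table 1, note e) then covers it without a new visit.

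The cost is one line in the protocol and one CRF item. A few former users would be screened out and replaced from the roughly 990 patients planned for the lead-in. Visits, assays, analysis and sample size do not change.
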